5.2. Efficacy Reporting

Secondary efficacy (clinical activity) endpoints will be summarized using IDSL standard reporting shells as indicated in Section 5.7.2. The following are considerations for handling and/or reporting secondary efficacy endpoints:

Clinical benefit rate and objective response rate in monotherapy group will be displayed using the All Treated Subjects Population and based on the disease assessment data up to crossover and prior to new anti-cancer therapy.

For the time to event efficacy endpoints (including DOR, PFS and Time to AML), crossover will be considered as censor situation (if no progressions before crossover) using the All Treated Subjects Population. The number of subjects with progression to AML will apply the same AML definition as the one used in time to event endpoint.

OS is defined as the time from first treatment dose until death due to any reason regardless of crossover using the All Treated Subjects Population.

Platelet and RBC transfusions will apply the same rule as CBR and ORR to present summaries by treatment group using the All Treated Subjects Population.

Objective response rate and Clinical benefit rate

This study employs response criteria from IWG criteria [Cheson, 2006] for response definition. The Clinical Benefit Rate (CBR) is defined as the percentage of subjects achieving a confirmed Complete Remission (CR) or Partial Remission (PR) or Marrow Complete Remission (mCR) or confirmed Hematologic Improvement (HI) or Stable Disease (SD) prior to new anti-cancer therapy and crossover on the All Treated Subjects Population.

Objective response rate is defined as the percentage of subjects who achieved CR or PR or mCR or HI prior to new anti-cancer therapy on the All Treated Subjects Population.

Subjects with Not Evaluable or missing response will be treated as non-responders; i.e. they will be included in the denominator when calculating the percentage.

The CBR and ORR will be reported for combined treatment group in Part 1 with the same drug and the same dose. Confirmed and unconfirmed response summaries will be provided. The number and types of responses, as outlined in IWG criteria [Cheson, 2006, also presented in the table below], will be produced, along with two-sided 95% exact confidence interval (CI).

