The CBR and ORR differences between the two cohorts will be provided along with corresponding two-sided 95% exact confidence interval (CI). A chi-square test will be used to test for differences between arms if the data warrant. Otherwise, a fisher's exact test will be employed if sample sizes are small at the beginning of trial.

IWG CRITERIA FOR RESPONSE

Category	Response Criteria
Complete Remission	
Bone marrow: $\leq 5\%$ myeloblasts with normal maturation of all cell lines^a
 
Persistent dysplasia will be noted^{a,b}
 
Peripheral blood (Response must be maintained for at least 4 weeks)
 
Hgb ≥ 11 g/dL
 
Platelets ≥ 100 Gi/L
 
Neutrophils ≥ 1.0 Gi/Lb
 
Blasts 0%

Partial Remission	All CR criteria if abnormal before treatment except: Bone marrow blasts decreased by $\geq 50\%$ over pre-treatment but still $>$

	5% Cellularity and morphology not relevant
Marrow CRb	Bone marrow: $\leq 5\%$ myeloblasts and decrease by $\geq 50\%$ over pretreatments Peripheral blood: if HI responses, they will be noted in addition to marrow CRb
HI	Erythroid (HI-E): hgb increase of > 1.5 g/dL decrease of $>$ RBC transfusions/8weeks versus pretreatment requirement in previous 8 weeks; only RBC transfusions given for a pretreatment Hgb of < 9.0 g/dL count Platelet (HI-P): increase of $> 30,000/\text{mL}$ (starting with $> 20,000/\text{mL}$) increase from $< 20,000/\text{mL}$ to $> 20,000/\text{mL}$ by $> 100\%$ Neutrophil (HI-N): increase of $> 100\%$ and $> 500/\mu\text{L}$
Stable Disease	Failure to achieve at least PR, but no evidence of progression > 8 wks
Disease Progression	For subjects with:  Less than 5% BM blasts: $\geq 50\%$ increase in blasts to $> 5\%$ blasts  5%-<10% BM blasts: $\geq 50\%$ increase to $> 10\%$ blasts  10%-<20% BM blasts: $\geq 50\%$ increase to $> 20\%$ blasts  20%-30% BM blasts: $\geq 50\%$ increase to $> 30\%$ blasts Any of the following:  At least 50% decrement from maximum remission/response in granulocytes or platelets  Reduction in Hgb by $\square 2$ g/dL  Transfusion dependence
Non-evaluable	Subject does not meet any of the above criteria

BM = bone marrow ; CR = complete remission; Hgb = hemoglobin;; PR = partial remission

a. Dysplastic changes should consider the normal range of dysplastic changes (modification).

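### Three of the HI limbs in SAP section 5.2 need neither an abnormal pre-treatment value nor a minimum duration, which can inflate ORR and start DOR on a rise that is not a response

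*SAP*

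**What the plan says.** The response table in SAP section 5.2 gives HI five limbs.

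- **Haemoglobin:** "Erythroid (HI-E): hgb increase of > 1.5 g/dL decrease of". The rise is the whole rule; the closing words begin the transfusion limb.
- **RBC transfusion:** a reduction in "RBC transfusions/8weeks versus pretreatment requirement in previous 8 weeks; only RBC transfusions given for a pretreatment Hgb of" below 9.0 g/dL.
- **Platelets, higher start:** "Platelet (HI-P): increase of" more than 30,000, starting above 20,000.
- **Platelets, lower start:** from below 20,000 to above 20,000, by more than 100%.
- **Neutrophils:** "Neutrophil (HI-N): increase of" more than 100% and more than 500/µL.

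Other rows of the table are stricter. PR begins "All CR criteria if abnormal before treatment except", so it refers to the entry value. For CR, the peripheral blood entry says "Response must be maintained for at least 4 weeks". Stable disease needs more than 8 weeks without progression.

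The rates are defined just before the table. For ORR: "Objective response rate is defined as the percentage of subjects who achieved CR or PR or mCR or HI". The word confirmed is absent. CBR, by contrast, lists "confirmed Hematologic Improvement (HI) or Stable Disease (SD) prior to new anti-cancer therapy and crossover". The section plans both confirmed and unconfirmed summaries, which are Tables 2.2 and 2.1, and each carries ORR and CBR. DOR runs from the first documented evidence of response and lists HI without the word confirmed. The SAP nowhere says what confirms an HI.

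**The concern.** HI alone makes a subject an objective responder. A rule based only on change then counts two kinds of subject who have not had a haematologic response in any useful sense:

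- a subject whose lineage needed no improvement at entry;
- a subject whose count rose once, through ordinary variation, an infection or a recent transfusion.

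Both errors add responders and remove none, so the bias in ORR is upward. A false HI also starts the DOR clock, so DOR would include durations for subjects with no response to lose. The PR wording shows that the table allows for subjects who enter with some values not abnormal, so such subjects are not excluded by construction.

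**Working it through.** The SAP states no rate, sample size or power on this point, so there is no figure to reproduce. The check applies the row literally, follows the result through the endpoint definitions, and then illustrates its size on assumed inputs.

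**1. Conditions stated, row by row**

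| Row or limb | Entry condition | Duration or window |
|---|---|---|
| CR | not stated | at least 4 weeks |
| PR | yes, if abnormal before treatment | through the CR criteria |
| HI, haemoglobin | none | none |
| HI, RBC transfusion | yes, Hgb below 9.0 g/dL | 8 weeks against previous 8 weeks |
| HI, platelets from above 20,000 | none (no upper limit) | none |
| HI, platelets from below 20,000 | yes | none |
| HI, neutrophils | none | none |
| SD | not applicable | more than 8 weeks |

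**2. Literal application to subjects normal at entry** (platelets read on the scale where 30,000 is 30 Gi/L)

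- Hgb 13.0 to 14.6 g/dL: 14.6 − 13.0 = 1.6, above 1.5. HI.
- Platelets 200,000 to 235,000: rise 35,000, above 30,000, and start above 20,000. HI.
- Neutrophils 2,000 to 4,100/µL: rise 2,100, above 500, and 2,100/2,000 = 105%, above 100%. HI.

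Each entry value is above the CR threshold in the same table (Hgb 11 g/dL, platelets 100 Gi/L, neutrophils 1.0 Gi/L).

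**3. Where such a subject is counted**

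| Output | One raised count | Repeated rise, lineage normal at entry |
|---|---|---|
| ORR as worded in 5.2 | counts | counts |
| CBR as worded in 5.2 | does not count (needs confirmed HI) | counts |
| Table 2.1 (unconfirmed), ORR and CBR | counts | counts |
| Table 2.2 (confirmed) | does not count | counts |
| DOR start | starts the clock | starts the clock |

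Confirmation therefore deals with the single count but not with the normal entry value.

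**4. Illustration of size. All inputs here are assumptions, not in the SAP.**

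*Platelets.* True value stable at 200 Gi/L, within-subject CV of 8%, 10% or 15%, so SD = 16, 20 or 30. Baseline and each later count are independent and normal. For one later count, P(rise > 30) = 1 − Φ(30 / (√2 × SD)):

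- SD 16: 30/22.6 = 1.33, giving 0.092
- SD 20: 30/28.3 = 1.06, giving 0.144
- SD 30: 30/42.4 = 0.71, giving 0.240

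For at least one of four later counts: 0.243, 0.347 and 0.506.

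*Haemoglobin.* No true change, 400,000 simulated subjects. The table shows the chance of a false HI from any single value against two consecutive values.

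| SD (g/dL) | 4 values: single / two | 8 values: single / two |
|---|---|---|
| 0.5 | 5.5% / 0.7% | 9.0% / 1.3% |
| 0.75 | 21.1% / 4.8% | 30.9% / 8.4% |
| 1.0 | 34.6% / 10.6% | 47.2% / 17.4% |

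Each false HI adds 1/n to ORR; with an assumed n of 10, that is 10 percentage points.

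**The case against.** **The cited criteria may supply the missing conditions.** Section 5.2 says the study uses the 2006 IWG criteria, so the printed table might be only a summary of them. This does not settle the matter. The section says those criteria are presented in the table, footnotes mark parts of the table as modified, and Tables 2.1 and 2.2 carry a different label (IMWG 2016). A programmer cannot tell whether a condition was removed on purpose or left to a source.

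**Investigators assess response.** They may well discount an obviously spurious rise. That could reduce the problem in practice, but the SAP gives no rule for it.

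**The size is assumed.** This stands. The SAP gives no baseline counts and no number of subjects, and does not show that anyone entered with a normal lineage.

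**Impact is limited.** This also stands. These are secondary endpoints in a terminated study with one displayed group, Tables 2.1 and 2.2 carry no p-value, and Listing 27 shows individual responses.

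A reader might also infer more than the text supports:

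- *That the whole HI row lacks an entry condition.* It does not: the RBC-transfusion limb and the platelet limb starting below 20,000 each have one.
- *That one raised count makes a CBR responder throughout.* Only in Table 2.1. The CBR definition and Table 2.2 require confirmed HI. A stable subject followed beyond 8 weeks is already in CBR as SD, so a false HI adds to CBR only for a subject who would not otherwise reach SD.
- *That the transfusion limb omits the number of units.* The printed line shows none, but it may have been lost when the PDF was read, so it carries no weight here.
- *That the 8 weeks in the table is already an HI duration.* In the HI row it is a window for counting transfusions, and in the SD row a minimum time without progression.

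**Conclusion.** The point holds for three limbs: haemoglobin, platelets from above 20,000, and neutrophils. Followed as printed, they class a subject with a normal lineage at entry as an HI responder in both the confirmed and the unconfirmed tables. A single raised count suffices for ORR as worded, for Table 2.1 and to start DOR. The consequence falls mainly on ORR and DOR, and the bias in ORR can only be upward.

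The size cannot be estimated from the SAP. The illustrative probabilities (9% to 24% for one platelet count, 24% to 51% for any of four) show that ordinary variation could trigger the rule in a subject normal at entry. They do not predict this study's rates, and the SAP does not support saying that such subjects dominate the results. The change should be made before the response tables are produced, but it does not touch the primary safety endpoints.

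**What to change.** In the HI row of section 5.2:

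1. Limit the haemoglobin, higher-start platelet and neutrophil limbs to subjects whose pre-treatment value in that lineage was abnormal. The limit could be the CR thresholds in the same table (Hgb below 11 g/dL, platelets below 100 Gi/L, neutrophils below 1.0 Gi/L) or the entry limits of the response criteria the study adopts. State which.
2. State a minimum duration for HI, and say that meeting it is what confirmed HI means.
3. State that values supported by transfusion do not count.

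In the endpoint definitions, use confirmed in the same way for ORR, CBR and DOR. Keep Table 2.1 as the explicitly unconfirmed summary.

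Apply the revised rule to Tables 2.1, 2.2 and 2.4 and to Listing 27. In Table 2.1 the entry condition and the transfusion exclusion apply, but not the duration.

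The cost is SAP wording and a modest derivation. Haematology and blood-product data are already reported (Table 3.5, Listings 13 and 14). If HI stays investigator-assessed, the derivation can serve as a check on the recorded response. ORR may come out lower.

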b. Modification to IWG response criteria [[Cheson](#), 2006].

Progression-free Survival

Progression-free survival (PFS) is defined as the time from first treatment dose until the first documented sign of disease progression or death. For the analysis of Progression-free survival (PFS), if the subject received subsequent anti-cancer therapy or crossed over from monotherapy to combination therapy prior to the date of documented events, PFS will be censored at the last adequate assessment prior to the initiation of anti-cancer therapy and crossover. If the subject missed more than one visit prior to the date of documented events, PFS will be censored at the last adequate assessment prior to missing. Otherwise, if the subject does not have a documented date of events, PFS will be

censored at the date of the last adequate assessment. The description of PFS could be summarized as Table 1 using the All Treated Subjects Population.

Table 1 Progression-free Survival

Situation	Date of Progression or Censoring	Outcome
No baseline disease assessments	Date of first dose	Censored
No post-baseline disease assessments	Date of first dose	Censored
Crossover before progression	Date of disease assessment prior to crossover	Censored
Progression documented between scheduled visits	Date of disease assessment	Progressed
No progression	Last date of disease assessment	Censored
New anticancer treatment started	Date of disease assessment prior to initiation of anti-cancer therapy	Censored
Death before first PD assessment	Date of death	Progressed
Death between adequate assessment visits	Date of death	Progressed
Death or progression after more than one missed visit	Date of disease assessment prior to missed visits	Censored

Duration of Response

Duration of response is defined as the subset of subjects (responders) who show a response (CR, mCR, PR, or HI), the time from first documented evidence of response until the first documented sign of disease progression or death. If no disease progression or death, the DOR will be censored at last disease assessment. The same censoring and event rules for PFS will be applied for DOR using the All Treated Subjects Population.

Overall Survival

Overall survival (OS) is defined as the time from first treatment dose until death due to any reason. For the analysis of overall survival (OS), the last date of known contact will be used for those subjects who have not died at the time of analysis; such subjects will be considered censored.

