AML Progression

The proportion of subjects with disease progression to Acute Myeloblastic Leukemia (AML) is defined as the percentage of patients experiencing AML on the All Treated Subjects Population. The number of patients experiencing progression due to AML will be summarized using the All Treated Subjects Population as well. Time to AML progression is defined as the time from first treatment dose until AML progression or crossover if using the All Treated Subjects Population. For the analysis of time to AML,

if the subject did not experience AML, time to AML will be censored at the last treatment prior to the initiation of anti-cancer therapy or crossover.

Documented Platelet and RBC Transfusions

The number and percentage of documented platelet and RBC transfusions per month prior to study entry and during the treatment period will be produced on the All Treated Subjects Population. The number of transfusions will be summarized on the data up to crossover for monotherapy treatment on the All Treated Subjects Population.

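### Time to AML censors AML-free subjects at last treatment, unlike PFS and DOR, and sets no cut-off for AML after new anti-cancer therapy

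*SAP*

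**What the plan says.** Section 5.2, under AML Progression, gives the endpoint as follows: "Time to AML progression is defined as the time from first treatment dose until AML progression or crossover". For subjects without AML it adds that "time to AML will be censored at the last treatment prior to the initiation of anti-cancer therapy or crossover". That sentence is conditional on the subject not having had AML. Nothing else in Section 5.2 confines AML events to the treatment period or says how to treat AML first documented after new anti-cancer therapy.

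The sister endpoints use another date. Under Progression-free Survival, when new therapy or crossover comes first, "PFS will be censored at the last adequate assessment prior to the initiation of anti-cancer therapy and crossover". The matching row of Table 1 for new treatment gives "Date of disease assessment prior to initiation of anti-cancer therapy" with outcome censored. Without an event, PFS stops at the last adequate assessment and duration of response at the last disease assessment. The PFS rules are extended to duration of response, but not to time to AML.

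Two general statements at the start of Section 5.2 also apply. For the time-to-event endpoints, time to AML included, "crossover will be considered as censor situation (if no progressions before crossover"). On the count, "The number of subjects with progression to AML will apply the same AML definition as the one used in time to event endpoint". The crude AML proportion "is defined as the percentage of patients experiencing AML on the All Treated Subjects Population".

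**The concern.** A dosing date does not show that a subject was free of AML on that day or stayed free afterwards. Under this rule a subject without AML leaves the risk set at the last dose, while a subject with AML stays in until the AML date, even if that is well after the last dose. Counted follow-up then depends on the outcome being measured, which a time-to-event analysis should avoid.

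The second gap concerns events. A subject whose AML follows new anti-cancer therapy did experience AML, so the censoring sentence does not reach that subject. For PFS the same event would be censored. Two programmers could handle such a case differently and both comply with the text.

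Frequency of and time to AML is a secondary objective (Section 2.1.1). Table 2.6 is marked for FDAAA and EudraCT (Section 5.7.2), in a plan written for the synoptic report and/or regulatory disclosure (Section 1).

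**Working it through.** The SAP gives no AML rate, sample size, assessment schedule or length of follow-up, so there is no figure to reproduce. The check therefore asks when the rule changes the estimate, and in which direction.

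**Assumptions.** Table 2.6 reports a Kaplan-Meier estimate (its shell, TTE1a, is not shown). AML is established at disease assessments; Section 2.1.1 says only that it follows the 2006 IWG criteria. Times are in months. A subject censored on the AML date counts as at risk on that date.

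**Formula.** With one AML event, at time t, the estimated cumulative AML just after t is 1/n(t). Here n(t) is the number of subjects whose counted time is at least t, including the subject with AML.

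**When n(t) changes.** An AML-free subject counts up to the last dose as written, and up to the last assessment under the PFS-style date.
- Last dose < t ≤ last assessment: the subject is missing from n(t) as written, so the estimate is too high.
- Last assessment < t ≤ last dose: the subject is in n(t) as written without having been assessed that late, so the estimate is too low.
- Otherwise that subject makes no difference.

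**Constructed examples**, six subjects and one AML each. Pairs are (last dose, last assessment) for the five AML-free subjects.

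| Example | AML-free subjects | AML at t | At risk, as written | At risk, last assessment | Estimates |
|---|---|---|---|---|---|
| Upward | (1,3), (2,4), (2,5), (3,5), (4,6) | 4 (last dose 2) | 1+1 = 2 | 4+1 = 5 | 1/2 = 50% vs 1/5 = 20% |
| No change | (5,6), (5,6), (5,6), (6,6), (6,6) | 4 (last dose 2) | 5+1 = 6 | 5+1 = 6 | 1/6 = 16.7% vs 16.7% |
| Downward | (4,2), (4,2), (4,4), (5,4), (6,6) | 3 | 5+1 = 6 | 3+1 = 4 | 1/6 = 16.7% vs 1/4 = 25% |

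The crude proportion is 1/6 = 16.7% in every row, because it does not use the censoring date. The second row shows that AML found off treatment is not enough to move the estimate: an AML-free subject must also have stopped dosing before that date and still be assessed on or after it. The third row shows that the estimate can move even without AML capture after the last dose, if dosing runs past assessment.

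**The event gap.** If the single AML in such a set came after new anti-cancer therapy, the time-to-AML analysis would hold one event on a literal reading of the AML paragraph and none under the PFS rule. The text does not settle which is meant.

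**Crossover.** The general rule makes crossover a censoring situation for time to AML, so AML after crossover is not open in this way. The AML paragraph's definition nevertheless names crossover alongside AML progression, as if it were an endpoint. That is a matter of wording.

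**The case against.** The strongest reply is that the bias turns on facts a SAP commonly leaves to the protocol: how often disease is assessed, and whether AML is captured after the last dose. On the SAP alone one can show an inconsistent date, but not a biased result. That stands, and it is why no size is claimed here. It does not remove the point, because the SAP itself fixes the censoring date, and fixes it on a basis that can distort the estimate in either direction.

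It can also be said that endpoints need not share a censoring date; overall survival, for example, uses last known contact. True, but last contact is when the subject is known to be free of that event. Last dose is not the corresponding date for AML. The SAP does not state how AML is ascertained, and its response table has no AML category, so ascertainment by disease assessment is an inference, though a natural one given the IWG reference.

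A reader might infer three stronger things that the document does not support:
- That the rule inflates AML. It may also deflate it or change nothing.
- That AML after crossover is uncapped too. The general rule in Section 5.2 already censors at crossover.
- That the reported AML frequency is wrong. The crude proportion does not depend on the censoring date. Requiring the same AML definition for the count may mean the same diagnosis rather than the same time window, so the count needs clarifying, not correcting.

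**Conclusion.** The point holds as an inconsistency worth fixing. The date used for AML-free subjects does not match the way the endpoint is likely to be observed or the rules for PFS and duration of response, and AML after new anti-cancer therapy has no cut-off. Direction and size for this trial cannot be derived from the SAP. The 50% against 20% and 16.7% against 25% contrasts are constructed to show that both directions are possible in a small dataset; they are not predictions, and they assume a Kaplan-Meier summary.

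The consequences are limited. One descriptive secondary display, Table 2.6, is affected, in a prematurely terminated study reported as a single group (Section 5). No test or decision rests on it.

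**What to change.** In the AML Progression paragraph of Section 5.2:

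1. Censor AML-free subjects at the last adequate disease assessment before new anti-cancer therapy or crossover. If neither occurred, use the last adequate assessment overall. With no post-baseline assessment, use the date of first dose, as in Table 1.
2. In the time-to-AML analysis, censor AML first documented after new anti-cancer therapy at that same assessment, as for PFS.
3. Bring the definition into line with the general rule by no longer naming crossover as an endpoint.
4. Leave the crude AML proportion as defined, and state whether the AML count includes AML after new therapy.

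The cost is two or three sentences and a small programming change. The assessment, new-therapy and crossover dates are already needed for PFS, so no new data are required. The downside is that AML after new therapy drops out of the time-to-AML summary; it can be listed separately.
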